#### 4.4 Withdrawal and discontinuation

Participants may be withdrawn from the study under the following circumstances:

- 1. **Withdrawal of informed consent**: If a participant decides to withdraw their consent at any point during the study, they will be removed from the study immediately.
- 2. **Disease progression or onset**: If a participant experiences significant disease progression or develops a new health condition that impacts their ability to participate in the study or could pose a safety risk, they may be withdrawn.

In the event of withdrawal, no further procedures will be conducted. Data collected up until that point will be anonymized by replacing any personally identifiable information with the unique participant code. If the participant requests, their name will be deleted, and only the unique code will remain associated with the data. This ensures that the participant's request is respected while preserving the integrity of the study data for future analysis.

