#### 3.2 Primary and secondary outcomes

#### **Primary outcome**

Uptake and feasibility of recruitment and research procedures

Uptake will be assessed both quantitatively and qualitatively. The quantitative assessment will include the range and average number of sessions attended by participants, as reported by cultural facilitators, while the qualitative assessment will explore reasons for non-attendance and barriers to engagement among participants. To enhance practicality, attendance will be measured based on sessions attended with the link worker, alongside standardized measures of the types of cultural activities recommended and attended, and self-reported participation in these activities. Feasibility of recruitment procedures will be evaluated by measuring the time required to recruit 100 participants, the number of individuals screened, and the number of eligible individuals who chose not to participate, as reported by GPs. Feasibility of research procedures will be assessed through the proportion of participants who complete follow-up assessments at each timepoint and the extent of missing data at both baseline and follow-ups. These measures will provide insights into the practicality of implementing the intervention and conducting research within this population. A measure of uptake will also be applied to the control group to evaluate if they did independently engage in cultural activities.

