A qualitative sub-study will be nested within the main study to explore the feasibility, acceptability, and experiences of participants, link workers, and general practitioners. A total of 28 voluntary participants will be interviewed, including family physicians (n=10), link workers (n=3), and study participants (n=15). The qualitative study aims to capture subjective experiences of the artistic and cultural prescription intervention and its perceived impact on health and the patient-physician relationship. Participation will be voluntary, and data collection will continue until thematic saturation is reached. Participants will be contacted by the Institute of Family Medicine and invited to take part to an optional interview. Interviews will be offered at both the first and second follow-up, with second follow-up interviews available only to those who did not participate in the first round. Efforts will be made to include individuals from diverse demographic backgrounds, health conditions, genders, and age groups. Separate semi-structured topic guides will be developed for each stakeholder group (see the document "Griglia intervista" for an overview of the topics that will be addressed with study participants). Physicians will be asked about recruitment processes and their experiences with the intervention, while link workers will provide insights into barriers and facilitators of engagement. Participants will discuss their experiences, including any barriers to participation, whether they found the programme enjoyable and beneficial for their symptoms, and if so, why. Interviews will be audio-recorded with participants' consent. Thematic analysis will be performed on the transcriptions of the interviews following Braun and Clarke's approach.

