#### Follow up of (Serious) Adverse Events

Participants who terminate the study with ongoing (Serious) Adverse Events (SAEs) will be asked to participate in a final assessment.

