#### 7 FURTHER ASPECTS

#### 7.1 Overall ethical considerations

The study will be conducted in accordance with **ethical guidelines**, with approval sought from the Ethics Committee of the Canton of Ticino. Participants' confidentiality and rights will be protected throughout the study.

Data will be systematically uploaded for analysis to **SwitchDrive**, a secure data storage system. Participants will each be assigned a unique identifier, and quantitative data from the questionnaires will be entered into an **Excel spreadsheet** by a designated researcher and subsequently checked for accuracy by a second researcher.

Informed consent will be obtained in writing before participation, ensuring that participants understand their right to withdraw from the study at any time without any consequences to their medical care. To minimize potential biases and preserve the integrity of the data, participants will not be informed in advance whether they are assigned to the experimental or control group. Instead, they will be provided with a general explanation of the study's objectives and the existence of two groups with different activities, without specifying the nature of each group's participation. At the conclusion of the second follow-up, participants will be fully debriefed about the study design and group allocation. This approach is in line with Article 18 of the Federal Act on Research involving Human Beings. Participants will receive an appropriate debriefing both

orally and in written form, and will be asked to provide written informed consent to the use of their data.

The **well-being of participants** will be the primary concern throughout the study. Any adverse effects or unintended consequences arising from participation in the event will be monitored and addressed promptly. Participants will be provided with support resources if needed, especially if their involvement leads to unexpected emotional or psychological responses.

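### Section 4.4 ends every study procedure for participants withdrawn for worsening health who still consent, so their remaining health outcomes and, before 6 months, their interviews go uncollected

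*Protocol*

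**What the plan says.** Section 4.4 lists two grounds for withdrawal from the study.

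- Consent: "If a participant decides to withdraw their consent at any point during the study, they will be removed from the study immediately".
- Health: the ground is significant disease progression, or that a participant "develops a new health condition that impacts their ability to participate in the study or could pose a safety risk, they may be withdrawn".

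The same consequence follows in both cases: "In the event of withdrawal, no further procedures will be conducted". Data collected up to that point are kept under the participant code.

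Four other places bear on this.

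- Section 3.2 makes reasons and barriers part of the primary outcome: "the qualitative assessment will explore reasons for non-attendance and barriers to engagement among participants". It also lists health measures, consultations and hospital or emergency use as secondary outcomes. The last two come from a GP questionnaire sent after the final follow-up.
- Section 3.3 fixes when interviews happen: "Interviews will be offered at both the first and second follow-up". The planned number for participants is 15.
- Section 6.2 says: "Participants who terminate the study with ongoing (Serious) Adverse Events (SAEs) will be asked to participate in a final assessment".
- Section 7.1 says that, with the debriefing, participants "will be asked to provide written informed consent to the use of their data".

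**The concern.** Stopping procedures is what one expects when consent is withdrawn. It is not needed when someone becomes too ill for the programme but is still willing to answer questionnaires or be seen. Section 4.4 treats the two alike, so a participant can leave the outcome data because of the very thing being measured.

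Section 5.1 names paired t-tests for the pre-post comparison, and these use only people with a follow-up value. Mixed models are mentioned only as a possibility. They would use partial data, but on a missing-at-random assumption that withdrawal for worsening health puts in doubt. The sensitivity analysis in Section 5.2 cannot restore values that were never collected. Whether to go on collecting is settled in the protocol, not in an analysis plan.

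Two things are at stake: secondary health results that look somewhat too favourable and feed the planning of the later randomised trial, and the first-hand accounts of some people who left early, who have something direct to say about barriers.

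**Working it through.** The protocol states no dropout rate, effect size, SD or power, so there is no figure of its own to reproduce. The check has two parts: what the text removes, and how large the effect could be on assumed values.

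**1. What is lost, and for whom**

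- Withdrawn for health before 6 months: both follow-up assessments and any interview, since interviews begin at the first follow-up.
- Withdrawn for health between 6 and 12 months: the 12-month assessment. An interview may already have taken place.
- GP questionnaire: unclear. Section 3.2 ties it to the last follow-up, and Section 4.4 does not say whether it counts as a procedure.
- Not attending, but not withdrawn: nothing. These participants meet neither ground in Section 4.4 and stay in follow-up.

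**2. Bias in one arm's mean change**

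Let w be the share withdrawn, C the mean change in completers and L the mean change those withdrawn would have shown. The full-arm mean is (1 − w)C + wL, so

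completer mean − full-arm mean = w × (C − L).

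The multiplier is the gap between completers and those withdrawn, not the decline of those withdrawn. The two agree only if completers do not change on average. With assumed inputs, in SD units:

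- w = 5%, gap 0.5: 0.05 × 0.5 = 0.025, about 0.03
- w = 15% (12 of 80), gap 0.8: 0.15 × 0.8 = 0.12
- w = 20% (16 of 80), gap 0.8: 0.20 × 0.8 = 0.16

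Wider inputs, 5-30% and 0.25-1.0 SD, run from 0.05 × 0.25 = 0.013 to 0.30 × 1.0 = 0.30. If those withdrawn fare worse, the error is in the favourable direction.

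**3. Bias in the between-arm contrast**

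With the same gap in both arms, bias = (w_exp − w_ctrl) × gap.

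- 20% v 20%: 0
- 20% v 5%, gap 0.5: 0.15 × 0.5 = 0.075 SD
- 30% v 5%, gap 0.5: 0.25 × 0.5 = 0.125 SD

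For scale, 80 v 20 with two-sided 5% and 80% power (both assumed) detects (1.96 + 0.84) × √(1/20 + 1/80) = 2.80 × 0.25 = 0.70 SD.

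**4. Interviews**

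If 15 interviewees were drawn at random from all 80 experimental participants (an assumption), the expected number of withdrawn people among them is 15 × m/80. For m = 4, 8, 16 and 24 (5%, 10%, 20%, 30%) that is 0.75, 1.5, 3.0 and 4.5. Under Sections 3.3 and 4.4, people withdrawn before 6 months supply none.

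**5. Passages that disagree**

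- Final assessment: Section 4.4 allows nothing after withdrawal. Section 6.2 asks people leaving with an ongoing adverse event to a last assessment, and Appendix 1 has no such visit.
- Debriefing: Section 4.3, item 7, places it when the individual's involvement ends. Section 3.3 places it after the study, and Section 7.1 and Appendix 1 after the second follow-up. Section 7.1 attaches the data-use consent to it, while Section 4.4 keeps early leavers' data without mentioning that step.

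**The case against.** The strongest reply is that the rule is narrower than it looks and the protocol has other safeguards. Much of that stands.

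- A reader might infer that everyone who stops attending is lost and that barriers will be described mainly by attenders. The documents do not support this. Health withdrawal is discretionary, non-attenders are encouraged to come to all assessments (Section 4.3) and they can be interviewed. Dropout reasons are recorded (4.3), reasons for not completing are summarised (5.1), link workers note barriers after each meeting (3.2), and 10 physicians and 3 link workers are interviewed (3.3). What these sources lack is an interview with the person who left.
- A reader might infer that none of the 15 interviews can come from someone withdrawn. Someone interviewed at 6 months and withdrawn later is a counterexample.
- A reader might infer heavier loss in the experimental arm, since weekly sessions ask more than a ticket does. That is plausible, but Section 4.4 speaks of ability to take part in the study, not in classes, and no document says that loss will differ by arm.
- A reader might infer that early leavers never reach the data-use consent. Section 4.3, item 7, would allow debriefing on leaving, so the fault is inconsistent timing.
- Section 6.2 gives some leavers a final assessment, so the loss is not total if that passage governs.

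The primary feasibility counts (sessions attended, retention, follow-up completion) also register withdrawals rather than lose them. The assumed biases are small beside the 0.70 SD that 80 v 20 could detect, and they concern secondary outcomes of a feasibility study. These points limit the weight of the concern. They do not explain why consenting participants who fall ill should have no further data collected.

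**Conclusion.** The point holds in limited form. By placing health withdrawal under the same stop rule as withdrawn consent, Section 4.4 discards follow-up from consenting people whose health has worsened, and interviews from those among them who leave before 6 months. The loss is likely to be informative for the secondary health outcomes and removes one first-hand source on barriers.

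Its size cannot be known from the protocol. The illustrative 0.03 to 0.16 SD for an arm's mean change rests wholly on the assumed withdrawal share and gap. The between-arm contrast is affected only if the share or the gap differs by arm. This is worth correcting before the study runs, because the correction is cheap and the data cannot be recovered afterwards, but it does not undermine the primary feasibility results.

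**What to change.** In Section 4.4, state that ending the activity, for whatever reason, does not end data collection unless consent is withdrawn. Such participants are still invited to the 6- and 12-month assessments (questionnaires alone if need be), and the GP questionnaire is still obtained. In Section 3.3, allow them to be offered one of the existing 15 participant interviews at the time they stop.

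Reconcile Section 4.4 with Section 6.2 and Appendix 1 on whether a final assessment takes place. Reconcile Section 4.3, item 7, with Sections 3.3 and 7.1 and Appendix 1 on when people who leave early are debriefed and asked for data-use consent.

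The cost is a few sentences and some extra contact with people who have stopped. The planned visits and the number of interviews do not rise. When the activity or participation should stop is left as it is.

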#### 5 STATISTICS AND METHODOLOGY

#### 5.1. Statistical analysis plan and sample size calculation

#### **Quantitative analysis**

Participant characteristics will be summarized at baseline to provide an overview of the sample. For all analyses, statistical significance will be set at p<0.05, but results will be interpreted based on the strength of the evidence, with continuous p-values and 95% confidence intervals (CIs) reported. Acceptability of the programme will be assessed through participant take-up and retention. The range and average number of sessions attended will be reported, along with a summary of reasons for not completing the intervention. Feasibility of recruitment and research procedures will be evaluated by assessing the time required to recruit 100 participants and analyzing the proportion of participants completing follow-up measures along with the amount of missing data at baseline and follow-up. Primary and secondary outcome measures will be summarized at baseline and follow-ups to assess changes over time. To evaluate the impact of the intervention, statistical methods such as paired t-tests will be used to compare pre- and post-intervention scores on health outcomes. Additional statistical approaches, including linear mixed-effects models or repeated-measures ANOVA, may be applied to account for individual variability over time. Gender will be analyzed as part of all statistical evaluations. All quantitative analyses will be performed using Stata or R. The

sample size of 100 participants is in line with similar feasibility studies in the field. Given that feasibility studies typically aim to assess the viability and practicality of an intervention rather than definitive outcomes, a sample size of 100 is appropriate for evaluating the key aspects of program implementation and data collection methods while providing insights for future larger-scale trials.

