#### 3 STUDY OBJECTIVES AND DESIGN

#### 3.1 Hypothesis and primary objective

Primary objective:

1. Explore programme feasibility and acceptability by assessing programme uptake, attendance

rates, reasons for non-attendance, and barriers to engagement.

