#### Secondary objectives:

- 2. Test whether there is any indication of an improvement in health orientation.
- 3. Compare health orientation and health outcomes of those participating in the programme versus the control group.

The study hypothesizes that cultural prescribing (artistic and cultural activities as part of healthcare) will be feasible and acceptable to older adults, and that participation in the program will lead to improvements in health orientation and health outcomes compared to a control group.

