#### **Secondary outcomes**

Health Orientation

To assess participants' health orientation, the Health Orientation Scale (HOS), a validated scale, will be administered at baseline and follow-ups. The HOS is designed to measure individual differences in health-related attitudes, beliefs, and behaviours. It assesses various psychological and behavioural aspects of how people perceive, manage, and respond to their health. Higher scores on the HOS generally indicate a stronger focus on health-related thoughts, emotions, and behaviours. However, the interpretation depends on the specific dimension being measured. The HOS is a comprehensive measure because it assesses multiple psychological and behavioural dimensions of health, including awareness, anxiety, motivation, control beliefs, social perceptions, and future expectations, providing a holistic understanding of an individual's health-related attitudes and behaviours.

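### A blanket p<0.05 rule and a directional hypothesis over an open set of health outcomes conflict with the protocol's own exploratory framing

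*Protocol*

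**What the plan says.** **The threshold.** Section 5.1 of the protocol reads "For all analyses, statistical significance will be set at p<0.05, but results will be interpreted based on the strength of the evidence", and the sentence ends "with continuous p-values and 95% confidence intervals (CIs) reported". The synopsis (Statistical Considerations) gives the same 0.05 level, with p-values and 95% confidence intervals as the basis for interpretation, but without the remark about strength of evidence. Section 5.1 also says "Gender will be analyzed as part of all statistical evaluations".

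**The hypothesis.** The primary objective in section 3.1 begins "Explore programme feasibility and acceptability by assessing programme uptake, attendance". The first secondary objective is "Test whether there is any indication of an improvement in health orientation", and the next compares health orientation and health outcomes with the control group. The closing hypothesis covers feasibility and acceptability, and adds that "participation in the program will lead to improvements in health orientation and health outcomes compared to a control group".

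**The framing.** Section 2 describes the health aim as exploring for signs of improvement. The synopsis calls between-group differences preliminary (Number of Participants) and promises only preliminary insights (Ethical consideration). Section 5.1 contrasts feasibility work with definitive outcomes, and section 7.2 speaks of preliminary impact.

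**The concern.** The hypothesis of benefit is attached to health orientation and to health outcomes as a whole. Nothing says which outcome counts, whether 6 or 12 months counts, or whether the pre-post change or the between-arm difference counts. Section 3.1 speaks of a comparison with control, whereas the impact test named in section 5.1 is a paired pre-post t-test, with mixed models or repeated-measures ANOVA as options. Health orientation is itself not one quantity: section 3.2 says of the scale that "it assesses multiple psychological and behavioural dimensions of health, including awareness, anxiety, motivation, control beliefs, social perceptions, and future expectations".

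With one threshold for everything, any result below 0.05 in the hoped-for direction can be reported as a significant improvement that supports the hypothesis. The study is meant to prepare a randomised trial. An endpoint or effect size carried forward because it had the smallest of several dozen p-values is likely to be partly chance.

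**Working it through.** **The plan's own figure.** The only error rate stated is 0.05 per analysis. There is no family-wise rate or power calculation to reproduce, since the 100 participants are justified by precedent.

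**Counting the tests (section 3.2, one variable per listed item).**
- Health Orientation Scale: 1
- Mental health and well-being questionnaires: 9
- Clinical and cognitive assessments (anthropometry, blood pressure, bioimpedance, Mini-Mental State, Clock Test): 5
- Wearable domains (heart rate variability, sleep, activity and stress): 3
- Blood markers: 5
- Urine markers (creatinine only normalises): 3
- Service use from the GP (consultations; hospitalisations or emergency accesses): 2

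Total: 1 + 9 + 5 + 3 + 5 + 3 + 2 = 28 measures. The first 26 are measured at two follow-ups and the GP items once, so 26 × 2 + 2 = 54 tests.

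The count is an assumption. Separate Health Orientation dimensions, extra wearable metrics, or both pre-post and between-arm contrasts would raise it. One overall effect per outcome from a mixed model would lower it to about 28.

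**Formulas.** Two-sided tests are assumed, because sidedness is not stated and 95% CIs are reported.
- Independent tests: the chance of at least one p<0.05 is 1 − 0.95^m in either direction and 1 − 0.975^m in the benefit direction.
- Tests with common correlation ρ, with z = 1.96: either direction, 1 − ∫ [Φ((z − √ρ·x)/√(1−ρ)) − Φ((−z − √ρ·x)/√(1−ρ))]^m φ(x) dx. For benefit only, the second Φ term is dropped.

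The protocol gives no correlations, so a range is shown.

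| Assumed ρ | 54 tests, either direction | 54 tests, benefit only | 28 tests, either direction | 28 tests, benefit only |
|---|---|---|---|---|
| 0 | 94% | 75% | 76% | 51% |
| 0.2 | 88% | 54% | 70% | 39% |
| 0.3 | 82% | 46% | 64% | 34% |
| 0.5 | 64% | 32.5% | 49% | 25% |
| 0.8 | 31% | 15% | 25% | 13% |

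For ρ = 0 and m = 54: 1 − 0.95^54 = 1 − 0.063 = 0.94, and 1 − 0.975^54 = 1 − 0.255 = 0.745.

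The expected number of false positives does not depend on correlation: 54 × 0.05 = 2.7 in either direction, of which 54 × 0.025 = 1.35 in the benefit direction.

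**Check on the correlation structure.** A simulation used 27 outcomes at two time points, with correlation 0.6 between times and 0 to 0.5 between outcomes (both assumed). It gave 92% down to 69% in either direction and 70% down to 36% for benefit only, which agrees with the table.

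**The case against.** **The health results are framed as exploratory.** This is true in several sections, and the 5.1 sentence itself tempers the threshold with strength of evidence, continuous p-values and confidence intervals. It would be wrong to say that the protocol carries no exploratory language. What it lacks is a statement that the p-values themselves are exploratory and cannot support a claim of effect. The blanket threshold and the 3.1 hypothesis pull the other way, and a reader cannot tell which governs.

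**Ordering of secondary outcomes belongs in a statistical analysis plan.** This stands as far as it goes. The absence of a hierarchy or an alpha adjustment in a pilot protocol is not the point made here. The point is what the protocol does fix: a significance rule for every analysis and a hypothesis of benefit. Health orientation has its own objective and is singled out in section 3.3, but it is not made the formal carrier of the hypothesis.

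**A reader might infer that a false finding of benefit is likely.** The documents do not support that as a general statement. The 64% counts apparent harms as well as apparent benefits. For benefit alone the figure at correlation 0.5 is about one in three, and with 54 tests it exceeds one half only when correlation is about 0.2 or lower.

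**A reader might also double the count to 108 for gender.** The protocol does not say that. Section 4.3 describes controlling for sex and gender by matching, and mentions model adjustment for confounders, so gender may enter only as a covariate. A test of gender difference would not show benefit in any case.

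**Conclusion.** The concern holds as a conflict within the protocol. Sections 5.1 and 3.1 set up confirmatory-style testing over an open set of outcomes, while the rest of the document treats the health results as exploratory.

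Under no effect, and on the 54-test assumption, a nominally significant result in some direction is more likely than not at correlations up to 0.5, but not at 0.8. A nominally significant benefit has a chance of about one in three at correlation 0.5. That is 0.325/0.025 = 13 times the single-test rate, and the range of 15% to 75% is 6 to 30 times. With about 28 tests the chance of a false benefit at correlation 0.5 falls to 25%. These sizes rest on the assumed test count, two-sided testing and the assumed correlations.

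The primary feasibility and acceptability outcomes are descriptive and do not depend on this rule. The point therefore limits what may be concluded about health effects, not the study's main purpose.

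**What to change.** 1. In section 5.1 and the synopsis, remove the 0.05 rule for all analyses. State instead that all health-outcome and gender analyses are exploratory, are reported as estimates with 95% CIs (continuous p-values optional), use no significance threshold and support no claim of effectiveness.
2. In section 3.1, reword the hypothesis so that only feasibility and acceptability are hypothesised and effects on health orientation and health outcomes are to be estimated. Change the verb in the first secondary objective to match.

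Naming one lead health contrast is optional. It is not needed once the secondary analyses are all exploratory, and it would sit badly with that label.

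The cost is protocol wording only, with no change to data collection or sample size. The small downside is that the sponsor can no longer call individual secondary results significant.
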